3	12	7																				
4	16	10																				
5	20	12																				
6	24	15																				
7	28	17																				

Item	Definition
Success Criterion	Percentage responder for infusion parameter $p$ in cohort $c$ $R_{c,p}(\%) = \frac{100 * (\text{Number of responder for } p \text{ in cohort } c)}{\text{Number of subjects in the SAF for cohort } c}$ with the success criterion for any $R_{c,p}$ being fulfilled if $R_{c,p} \geq 33\%$ .
Start Date of Non-Response	Date of the next infusion after a subject was classified as non-responder.
Terms	
AE Rate per Infusion	Number of Adverse Events for a Particular PT / Number of Infusions Within Cohort
Baseline	Most recent non-missing value prior to or on the first study treatment dose date
Body Mass Index (kg/m  )	Body weight (kg) / Height (m) 
Compliance per Infusion (%)	(Actual amount per infusion/prescribed or planned amount per infusion)*100, where amount is dose (mg/kg) or volume (mL)
Duration of Event	End date of the event – start date of the event + 1
Elapsed Time Until Event	Event date – reference date
Local TEAEs	TEAEs identified by MedDRA high level terms “administration site reactions NEC”, “infusion site reactions”, and “injection site reactions”
Tolerability of an Infusion Parameter Within Cohort	Number of infusions without severe local reactions within cohort / number of infusions within cohort (irrespective of their validity); an infusion without severe local reactions is defined as no occurrence of a severe local reaction from the start date and time of an infusion until the start date and time of the next infusion or study end if this was the last infusion.
Treatment-Emergent	Event which started on or after the date (and time) of first administration of study treatment

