## 11.2 Non-Responder

If a subject is unable to tolerate a certain infusion parameter level (i.e., is a non-responder at that level), the subject will continue study participation at the highest individually tolerable infusion parameter level for the remaining full study duration to collect safety information.

If a subject is a non-responder at a certain infusion parameter level, data collected until the time of non-response will be taken into account for the analysis of response. Data collected at the individually tolerable infusion parameter level after the non-response in the subjects will not be included in the analysis of response but will be listed and flagged in the listing.

The start date of non-response is the start date of the next infusion after the subject has been classified as non-responder. If a subject is a non-responder at the last infusion parameter level, the start date of non-response will be missing as no further data will be collected after the last infusion parameter level.

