### 11.4 AEs

AEs starting on or after the date (and time if available) of the first administration of study treatment will be considered treatment-emergent AEs (TEAEs). This is the formal definition of a TEAE. It should be kept in mind that all subjects have been on a stable Hizentra® dose prior to study start.

When the AE start date is missing or partially missing, AEs will be assumed to be treatment-emergent, unless there is clear evidence (through comparison of partial dates) to suggest that the AE started prior to the first dose of study treatment. For the assignment of AEs within 72 hours after administration of treatment (temporally associated AEs), only AEs

with complete start dates will be considered. The start time will also be considered if available. AEs which start during infusion or within 72 hours after the end of an infusion will be considered temporally associated AEs.

Only TEAEs occurring until EOS visit will be included in the summary tables. All AEs will be listed.

For non-responder subjects at a certain infusion parameter level, AEs reported at the individually tolerable infusion parameter level after the non-response in the subject, i.e., AEs starting at or after the next infusion following the infusion leading to non-response, will be listed and flagged. These AEs will be analyzed separately from the AEs reported prior to that time.

AEs will be coded using the MedDRA version 20.0 or higher. AEs will be primarily classified by MedDRA PT. Analyses will be performed by SOC and PT. Aggregated incidences at SOC level and Any TEAE will also be provided.

Summaries of TEAEs will count the number of subjects, that is, subjects with multiple occurrences of the same PT will be counted once. Summaries of TEAEs will also include the number of events for each PT. Summaries will be presented for each infusion parameter and total within cohort. TEAEs will be assigned to the infusion parameter level under which they occurred. In the Total column within cohort, each subject will only be counted once with all events experienced.

AE rates per infusion will be calculated within cohort in the following way for each infusion parameter level:

- $$\text{AE Rate per Infusion} = \frac{\text{Number of Events for a Particular PT}}{\text{Number of Infusions}}$$

where number of infusions will be the sum of all infusions that subjects received within infusion parameter level irrespective of their validity as defined in Section 11.1.

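### SAP 11.4 sets aside AEs after non-response but not the matching infusions, so a by-level AE rate per infusion can be understated; the by-level exposure formula in 11.3 can also drop fall-back weeks

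*SAP*

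**What the plan says.** A subject who does not respond at a level stays in the study and goes back to a level tolerated before (Protocol 3.1, SAP 4.1 and 11.2). That lower level therefore collects a second block of infusions.

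**Events.** SAP 11.4, like Protocol 11.3.3, has AEs from this fall-back phase listed and flagged, and adds: "These AEs will be analyzed separately from the AEs reported prior to that time".

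**Infusions.** The by-level AE rate per infusion in SAP 11.4 is the number of events divided by the number of infusions. The latter is "the sum of all infusions that subjects received within infusion parameter level irrespective of their validity as defined in Section 11.1". Nothing divides that sum into infusions before and after non-response, and no denominator is named for the separate analysis.

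**Allocation.** The same section says "TEAEs will be assigned to the infusion parameter level under which they occurred", and SAP 7 agrees. On the cohort total it says "In the Total column within cohort, each subject will only be counted once with all events experienced".

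**Exposure.** SAP 11.3 ends exposure at level [i] at the earliest of three dates: 7 days after the last treatment at that level, the day before level [i+1] starts, or study completion. It has no term for a return to a lower level.

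**The concern.** A rate needs events and infusions from the same period. Here the events are cut at fall-back and the infusions, as written, are not. If a programmer follows both sentences literally, the fall-back infusions add to the denominator at the lower level and their events do not add to the numerator.

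The AE rate and the local reaction rate, per infusion and by level, are the first two secondary endpoints (SAP 4.2). They are read as a comparison across levels, so a shortfall at one level distorts the apparent step to the next.

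Per-subject percentages by level depend on the same choice. With later AEs out, a subject whose only AE at that level came during fall-back is not counted. With them in, fall-back subjects are observed at that level for longer than the others.

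The exposure formula raises a related problem: by-level subject-years and by-level infusion counts may describe different periods.

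**Working it through.** The documents give no figure for this point. The 50% used below comes from the sample-size section (Protocol 11.1, SAP 4.5). Its 94% reproduces: P(X ≥ 5 | n = 15, p = 0.5) = 0.9408. It is not in dispute.

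**1. Size of the mismatch.** Let E_pre be the events at a level before fall-back, and N_pre and N_post the infusions there before and after it. The literal rate is

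E_pre/(N_pre + N_post) = (E_pre/N_pre) × N_pre/(N_pre + N_post),

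so the shortfall against the matched rate is N_post/(N_pre + N_post).

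Assumptions: 15 subjects; 4 infusions per level; no dropout; everyone responds at level 1; switching after 4 weeks; 7.5 subjects (50%) fail somewhere above level 1. A level with all 15 subjects has N_pre = 15 × 4 = 60. Manual push gives the same ratios if fall-back subjects infuse as often as the others.

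| Failure pattern | Level returned to | N_post | Shortfall |
|---|---|---|---|
| 3 levels, 3.75 fail at each of levels 2 and 3 | Level 1 | 3.75 × 4 = 15 | 15/75 = 20% |
| 4 levels, 2.5 fail at each of levels 2 to 4 | Level 1 | 2.5 × 8 = 20 | 20/80 = 25% |
| Same | Level 2 | 2.5 × 4 = 10 | 10/70 = 14% |
| 4 levels, all 7.5 fail at 75 mL/h | 50 mL/h | 7.5 × 4 = 30 | 30/90 = 33% |
| Same | 25 mL/h | 0 | 0% |
| All fail at the last level | none | 0 | 0% |

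In the second pattern N_pre at level 2 is still 60, because all 15 subjects are treated there before anyone fails.

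By number of subjects instead of a 50% assumption, for 1, 3, 5 and 7 subjects of 15 falling back:

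- 8 fall-back infusions each (flow rate cohort, failing at 50 mL/h): the multiplier 60/(60 + 8m) is 0.88, 0.71, 0.60 and 0.52.
- 4 fall-back infusions each (volume cohort failing at 40 mL, or flow rate cohort failing at 75 mL/h): 60/(60 + 4m) is 0.94, 0.83, 0.75 and 0.68.

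If events and infusions are cut at the same date, or neither is cut, the per-infusion mismatch is zero.

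**2. Exposure for a subject who fails level 2.** Scheduled infusion days are 1 to 22 at level 1 and 29 to 50 at level 2. Level 1 then resumes from Day 57 to Day 106 (flow rate; completion Day 113) or Day 78 (volume; completion Day 85).

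*[i] read as a level:*
- Flow rate, level 1: min(106 + 7, 29 − 1, 113) − 1 + 1 = 28 days. Level 2: min(50 + 7, 113) − 29 + 1 = 29 days. Total 57 of 113.
- Volume, level 1: min(78 + 7, 29 − 1, 85) − 1 + 1 = 28 days. Level 2: min(50 + 7, 85) − 29 + 1 = 29 days. Total 57 of 85.

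*[i] read as a consecutive period:*
- Flow rate: 28 + 28 + (113 − 57 + 1 = 57) = 113 of 113.
- Volume: 28 + 28 + (85 − 57 + 1 = 29) = 85 of 85.

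**The case against.** The best reply is that the SAP does not prescribe a mismatch. Events are assigned to the level at which they occur, and the Total takes in all of a subject's events, so later AEs may be meant to stay in the main tables. Every AE summary table must also show a rate per infusion (SAP 11.4), so a separate table would need its own infusion count. Table shells and dataset specifications are separate documents and may hold the rule. This stands as far as it goes: the understatement is conditional. But the SAP presents itself as the complete description (Section 3), and the one by-level denominator that it gives is uncut. Two programmers could produce different values for a named endpoint.

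Four stronger readings are tempting, and the documents do not support them.

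- **Two contradictory cut-offs.** A reader might infer this because 11.4 refers to "AEs starting at or after the next infusion following the infusion leading to non-response" while 11.2 says "The start date of non-response is the start date of the next infusion after the subject has been classified as non-responder" and 2.2 says "Date of the next infusion after a subject was classified as non-responder". The full sentence in 11.4, however, is limited to AEs at the individually tolerable level after non-response. If the subject completes four weeks at the failed level, AEs there are outside that set; if the subject steps down early, the next infusion is the first at the fall-back level. Both rules can be read as the same date. For the last level, 11.2 explains that "the start date of non-response will be missing as no further data will be collected after the last infusion parameter level": there is no fall-back phase to cut. The wording should be aligned, but a contradiction is not shown.
- **Much larger shortfalls from level-1 failures.** These would need level-1 non-responders to continue at level 1. Protocol 3.1 and SAP 4.1 refer to a previously tolerated level, and there is no earlier planned one. No figure is given for that case.
- **A bias that always counts against the higher levels.** With all failures at 75 mL/h, the understated rate is at 50 mL/h and not at 25 mL/h, which flatters a higher level.
- **Harm to the primary endpoint.** SAP 11.2 keeps fall-back data out of the response analysis, and the responder denominator is the cohort's safety set.

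**Conclusion.** The point holds as a minor one. Taken literally, SAP 11.4 divides a cut numerator by an uncut denominator. On the illustrative assumptions the first-level rate is 20% too low with three levels and 25% too low with four (14% at the second level). It ranges from 0% when all failures are at the last level to patterns where a higher tested level is affected, such as 33% at 50 mL/h. These sizes rest on failure patterns that the documents do not give, and they apply only if later AEs leave the main tables while their infusions stay.

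The exposure formula, read by level as written, leaves out fall-back weeks: 57 of 113 or 57 of 85 days are assigned for a subject failing level 2. Exposure is not the denominator of any planned AE rate, and overall exposure is defined separately, so this affects only the by-level durations and subject-years.

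Tolerability in SAP 11.4 uses the same infusions in both parts and is sound. All the affected output is descriptive.

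**What to change.** - Define one analysis cut-off, the first infusion at the fall-back level, and use the same wording for it in SAP 2.2, 11.2 and 11.4 and in Protocol 11.3.3. A subject with no fall-back phase has no such date, and all of that subject's data belong to the main part.
- Apply it to events and infusions alike. Main by-level rates use events and infusions before the cut-off; the separate analysis divides later events by later infusions. State the same rule for the Total column and for per-subject percentages.
- In SAP 11.3, index exposure by consecutive period and report fall-back exposure separately by level, so that the days add up to overall exposure.
- Leave the tolerability measure as it is. If the shells or dataset specifications already hold the rule, repeat it in the SAP.

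The cost is a few SAP sentences, aligned wording in the protocol, and one date variable carried into the AE, infusion and exposure datasets; listings already flag data after non-response. Some by-level AE rates may become less favourable. No dose or clinical rule changes.

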3.1 Study Design and Rationale

This multicenter, open-label, parallel-arm, non-randomized study is designed to evaluate safety and tolerability of higher infusion parameters of IgPro20 in subjects with PID. The study will include 3 cohorts with a minimum of 15 subjects each as follows:

- Pump-Assisted Volume Cohort (weekly infusions): Volume per injection site of 25 mL up to 50 mL.
- Pump-Assisted Flow Rate Cohort (weekly infusions): Flow rate per injection site of 25 mL/hour up to 100 mL/hour.
- Manual Push Flow Rate Cohort (2 to 7 infusions per week): Flow rate per injection site of 25 to 30 mL/hour up to 120 mL/hour (equivalent of approximately 0.5 mL/minute up to 2 mL/minute; see [Table 1](#)).

Each cohort will test 3 infusion parameter levels (for Pump-Assisted Flow Rate Cohort – 4) for at least 4 weeks each over a duration of 12 weeks (for Pump-Assisted Flow Rate Cohort – 16 weeks). After the fourth week on each level, qualifying subjects (responders) will switch to the next infusion parameter level (eg, from 25 to 50 mL/h). During the study the weekly dose will remain unchanged (as prescribed by treating healthcare provider, usually within 100-200 mg/kg per week range); only the respective infusion parameter under evaluation will change. If a subject is unable to tolerate the respective infusion parameter level (ie, is a non-responder at that level, for definition see [Section 11.3.5](#)), the subject will continue study

[figure not shown]
participation at the individually previously tolerated infusion parameter level for the remaining full study duration, to collect safety information.

If a subject within the Pump-Assisted Cohort is able to perform ≥ 3 out of 4 (75%) valid infusions at a certain infusion parameter level, he/she will be considered to be a responder for this infusion parameter level (eg, completed 3 infusions with 50 mL/h means responder for 50 mL/h). Valid infusions do not need to be consecutive. Determination of a responder in the Manual Push Cohort is more complex due to the expected variable frequency of infusions per week for different subjects (see [Section 11.3.5](#) for further details). Valid infusions in this cohort also do not need to be consecutive. However, each subject needs to adhere to the same schedule (number of infusions per week) throughout the study.

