## 4 Study Design

### 4.1 Study Design

This multicenter, open-label, parallel-arm, non-randomized study is designed to evaluate safety and tolerability of higher infusion parameters of IgPro20 in subjects with primary immunodeficiency (PID). A target of 45 evaluable subjects (i.e., 15 subjects per cohort) is needed. Enrolled subjects will include a target of 14 (30%) pediatric subjects  $\leq 17$  years of age and a target of 9 (20%) obese subjects with body mass index (BMI) of  $\geq 30$  kg/m^2.

Pediatric and obese subjects may be distributed across any or all of the treatment cohorts without respect to balanced enrollment within the cohorts for these subpopulations..

Assignment to one of the cohorts will take place at the Screening visit and subjects cannot be

changed later to another cohort. The study will include 3 cohorts with a minimum of 15 subjects each as follows:

- Pump-Assisted Volume Cohort (weekly infusions): Volume per injection site of 25 mL up to 50 mL;
- Pump-Assisted Flow Rate Cohort (weekly infusions): Flow rate per injection site of 25 mL/hour (h) up to 100 mL/h
- Manual Push Flow Rate Cohort (2 to 7 infusions per week): Flow rate per injection site of 25 to 30 mL/h up to 120 mL/h (equivalent of approximately 0.5 mL/minute up to 2 mL/minute)

Each cohort will test 3 infusion parameter levels (for Pump-Assisted Flow Rate Cohort – 4 levels) for at least 4 weeks each over a duration of 12 weeks (for Pump-Assisted Flow Rate Cohort – 16 weeks). After the fourth week on each level, subjects may switch to the next infusion parameter level, if the current level has been tolerated (e.g., from 25 to 50 mL/h). During the study the weekly dose will remain unchanged (as prescribed by treating healthcare provider, usually within 100-200 mg/kg per week range); only the respective infusion parameter under evaluation will change. If a subject is unable to tolerate the respective infusion parameter level (i.e., is a non-responder at that level, for definition see Section 11.2), the subject will continue study participation at the individually previously tolerated infusion parameter level for the remaining full study duration, to collect safety information.

The final analysis to support the CSR will take place after all subjects have completed or terminated the study.

The schedule of assessments planned for the study can be found in the protocol.

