
 
• To evaluate the safety of pump-assisted IgPro20 infusions at higher infusion parameters (volume and flow rate).
 
• To evaluate the safety of manual push IgPro20 infusions.
 
• To evaluate the tolerability of higher infusion parameters of IgPro20.
 
	
 
• The rate of total adverse events (AEs) per subject and per infusion by cohort and by each of the infusion parameter levels within the cohort.
 
• The rate of local reactions per subject and per infusion by cohort and by each of the infusion parameter levels within the cohort.
 
• The time to onset of local reactions per subject and per infusion by cohort and by each of the infusion parameter levels within the cohort.
 
• Severity of local reactions per subject and per infusion by cohort and by each of the infusion parameter levels within the cohort.
 
• Duration of local reactions per subject and per infusion by cohort and by each of the infusion parameter levels within the cohort.
 
• For all cohorts: Tolerability of a certain infusion parameter, i.e. percentage of infusions per cohort by volume/flow rate subgroup experiencing no severe local reactions for each of the infusion parameter levels.
 

Objectives	Endpoints
Exploratory	

 
CCI [REDACTED]
 
[REDACTED]
 
[REDACTED]
 
[REDACTED]
 
	
 
CCI [REDACTED]
 
[REDACTED]
 
[REDACTED]
 

[figure not shown]

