**TFLs Format**

All ICH required data in the database will be presented in data listings.

Data will be displayed as described in this SAP and in the supporting, separate TFL shells document(s).

Tables will be presented by cohort and infusion parameter within cohort (Pump-Assisted Volume: Volume per Site 25 mL, 40 mL, 50 mL, and Total; Pump-Assisted Flow Rate: 25 mL, 50 mL, 75 mL, 100 mL, and Total; and Manual Push Flow Rate: 30 mL/h [0.5 mL/minute], 60 mL/h [1 mL/minute], 120 mL/h [2 mL/minute], and Total) as specified in the respective sections. As subjects may participate in more than one infusion parameter group, the total column may not be the sum of the infusion parameter columns. Subjects and events will be counted once in the total column. Events and assessments will be assigned to the infusion parameter level under which they occur. There will be total columns within cohorts, but no total column over cohorts. Details will be specified in the TFL shells document and in the corresponding SAP section.

Listings will include cohort and infusion parameter, site number, subject number, and basic demographics (age, sex, BMI at Screening). Events and assessments will be assigned to the infusion parameter under which they occurred or were assessed. In subject-level listings, the subjects will be assigned to the highest infusion parameter which they successfully reached. Listings will be presented for a specific analysis set or for all available data depending on the nature of the information listed. In the listings for all available data, a column will be inserted showing the smallest analysis set the subject is assigned to (hierarchy of analysis sets in terms of size/subset: SAF  $\leq$  FAS  $\leq$  ScAS, analysis sets may comprise the same subjects).

Unless otherwise stated, listings will be sorted by treatment status (not treated subjects followed by treated subjects), and within treatment status by cohort and infusion parameter, site-subject number, and by visit date and time or by event date and time. In case of partial dates, date sorting will be by year, month, and day. If any of these variables does not apply to a listing, then that listing will use only those variables which are applicable in the order given here.

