### 8.1 Missing Data

#### 8.1.1 Imputation of Non-Date Missing Data

Missing data occurs when any requested data is not provided, leading to blank fields on the collection instrument. These data will be indicated by the use of a “blank” in subject listing displays. Answers such as “Not applicable” and “Not evaluable” are not considered to be missing data and should be displayed as such.

Subjects with the designation of treatment relationship for AEs and serious AEs (SAEs) missing will have the worst realistic case assumed to impute the relationship: if relationship to study treatment is missing and the AE started on or after the first infusion of study treatment it will be assumed to be “Related” (worst case). If the AE with missing relationship to treatment started before the first infusion of study treatment, it will be considered as “Not Related” (realistic case). There will be no other imputation for missing data.

For variables which determine the proportion of subjects, all subjects in the SAF will be included in the denominator when calculating the percentages irrespective of whether their outcome may be missing.

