Each AE summary table will present the number of subjects, percentage of subjects based on the SAF, number of events, and AE rate per infusion.

One overview summary of TEAEs table with entries for:

- any TEAE;

- causally related TEAEs;
- temporally associated TEAEs within 72 h;
- causally related or temporally associated TEAEs within 72 h
- deaths;
- causally related deaths;
- serious TEAEs;
- causally related serious TEAEs;
- study discontinuation due to TEAE;
- causally related study discontinuation due to TEAE;
- study drug withdrawal due to TEAE;
- causally related study drug withdrawal due to TEAE;
- local TEAEs;
- causally related local TEAEs;
- maximum severity of TEAEs.

will be produced.

The following summary tables of TEAEs will be produced:

- by SOC and PT;
- SAEs by SOC and PT;
- by SOC, PT, and maximum severity (missing severity will be presented as separate category);
- by SOC, PT, and causality (missing causality will be considered “Related” as outlined in Section [8.1.1](#));
- by SOC and PT temporally associated within 72 hours after treatment;
- by SOC and PT causally related or temporally associated within 72 hours after treatment;

- time to onset of TEAEs (descriptive statistics and categories 0 days, 1 day, 2 days, 3 days, > 3 days);
- duration of TEAEs (descriptive statistics and categories 1 day, 2 days, 3 days, > 3 days);
- tolerability of the infusion parameter (number of infusions without severe local reactions / number of all infusions).

Time to onset of TEAE will be calculated as

TEAE start date and time – infusion start date and time.

For the categories, the time will be rounded to days.

Duration of TEAEs will be calculated as defined in Section 8.2.3.

Tolerability of a certain infusion parameter within a cohort will be calculated as

number of infusions without severe local reactions / number of infusions

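### By-level adverse event percentages have no level-specific subject base: on SAP 11.4's literal wording, subjects who never entered a level count as event-free there

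*SAP*

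**What the plan says.** SAP 11.4 assigns each TEAE to the level at which it occurred. On display it says: "Summaries will be presented for each infusion parameter and total within cohort". Each adverse event table then gives the number of subjects, the "percentage of subjects based on the SAF, number of events, and AE rate per infusion". SAP 6.3 defines the SAF once for the whole study, as FAS subjects with any full or partial dose. It is not defined by level. For variables expressed as a proportion of subjects, SAP 8.1.1 adds that "all subjects in the SAF will be included in the denominator when calculating the percentages irrespective of whether their outcome may be missing".

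Not every subject reaches every level. Protocol 3.1 says: "After the fourth week on each level, qualifying subjects (responders) will switch to the next infusion parameter level". SAP 4.1 says that "subjects may switch to the next infusion parameter level, if the current level has been tolerated". Under either rule, a subject who fails at a level goes back to the last tolerated one.

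For infusions, SAP 11.4 does state a level-specific base. The denominator of the adverse event rate is "the sum of all infusions that subjects received within infusion parameter level irrespective of their validity", and tolerability is handled the same way. Subject percentages have no matching sentence. SAP 9.1 does tabulate how many subjects entered each level, so the number needed will be available.

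These percentages bear on secondary endpoints. SAP 4.2 lists, for example, "The rate of local reactions per subject and per infusion by cohort and by each of the infusion parameter levels within the cohort".

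**The concern.** In a by-level column the numerator can only come from subjects who were infused at that level. If the denominator is everyone in the cohort's SAF, subjects who never reached the level are counted as exposed without an event. The percentage then falls as fewer subjects enter, and a higher level can look safer only because fewer people tried it.

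The cohort SAF is the right base for the responder percentage in SAP 11.1, where failing to reach a level is properly a non-response and the full denominator is conservative. For adverse events the same denominator works the other way and flatters the higher levels. Those are the levels the study exists to assess, and the highest successful one is to be recommended for the label.

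**Working it through.** **Plan figures.** The documents give no figure for this denominator. The nearest is the 94% in Protocol 11.1 and SAP 4.5. It reproduces: P(X ≥ 5) for a binomial with n = 15 and p = 0.5 is 0.9408. This confirms the 5-of-15 threshold used below and says nothing about adverse event percentages.

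**Inputs.** Cohort SAF N = 15 (planned size, Protocol 11.1). Success at a level needs at least 5 of 15 responders (Protocol 3.1). Entrants m and subjects with an event x are assumptions; the documents give neither.

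**Formula.** Printed percentage = x/N = (x/m) × (m/N), which is the percentage among exposed subjects times entrants over cohort SAF.

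| Entrants m | Factor m/15 | Example: exposed base | Same events, SAF base |
|---|---|---|---|
| 15 | 1.00 | 6/15 = 40% | 6/15 = 40.0% |
| 12 | 0.80 | 6/12 = 50% | 6/15 = 40.0% |
| 8 | 0.53 | 4/8 = 50% | 4/15 = 26.7% |
| 5 | 0.33 | 2/5 = 40% | 2/15 = 13.3% |

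**Order of levels.** Suppose 5 of 15 subjects have an event at the starting level (33.3%), and 4 of 8 entrants have one at the top level. The exposed base gives 50.0% at the top. The SAF base gives 4/15 = 26.7%, below the starting level, so the order reverses.

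**Which entrant numbers are plausible.**
- A level that meets the success criterion has at least 5 responders of 15, hence at least 5 entrants. At a level that could be recommended, the factor therefore lies between 0.33 and 1.00.
- The planning assumption of 50% response at the top level implies 15 × 0.5 = 7.5 expected responders, so at least that many expected entrants and an expected factor of at least 0.50.
- Suppose instead that the same fraction of entrants responds at every level, half the cohort responds at the top, and nobody withdraws. The fraction is 0.5^(1/4) = 0.841 with four levels, giving 15 × 0.841³ = 8.9 entrants at the fourth flow-rate level (factor 0.59). It is 0.5^(1/3) = 0.794 with three levels, giving 15 × 0.794² = 9.5 entrants at the third level (factor 0.63).
- At the starting level, and at any level that everyone enters, the factor is 1.00.

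**The case against.** The strongest reply is that SAP 11.4 uses the phrase to name a population and not to fix a denominator. SAP 9 and the opening of SAP 11 speak of tables and analyses being based on the SAF in just that sense. Where the SAP wants every cohort subject in the denominator, as for the responder percentage in SAP 11.1, it says so outright. Taken strictly, the SAF is study-wide, so even the cohort reading used above narrows it by context; a reader who narrows it once more, to the level, does no greater violence to the text. SAP 8.1.1 sits under missing data, and a subject who never entered a level has no missing outcome there. SAP 7 also treats levels as groups of participants: "As subjects may participate in more than one infusion parameter group, the total column may not be the sum of the infusion parameter columns". It leaves display details partly to the table shells, where column Ns would normally be set.

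Much of this stands. Shells with level Ns would not contradict SAP 11.4, so a reader should not infer that the final tables will necessarily be diluted. What remains is that no section states a level base for subject percentages, although SAP 11.4 states one for infusions, and the only general rule on denominators points to the full SAF.

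Two further inferences go too far. One is that by-level safety reporting as a whole is compromised. Subject counts, entrants per level, level-specific rates per infusion and level-specific tolerability are all planned, so the exposed-subject percentage can be worked out by hand. The other is that by-level percentages of valid infusions are diluted as well. The base given in SAP 11.1 can be read as infusions in the cohort or infusions at the level; the cohort reading would print far less than 100% for a level at which every infusion was valid, which is hardly the intention. That needs a clarifying word and is not a finding.

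**Conclusion.** The point holds as a gap in the SAP that should be closed. Followed literally and read at cohort level, SAP 11.4 with SAP 8.1.1 multiplies each by-level subject percentage for TEAEs and local reactions by entrants over cohort SAF. The factors of 0.80, 0.53 and 0.33 rest on a cohort of 15 and on assumed entrant numbers of 12, 8 and 5. The effect depends wholly on how many subjects do not advance.

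The consequence is limited. The responder percentage, and with it the label rule, is unaffected, as are the adverse event rate per infusion and tolerability. No hypothesis is tested. The exposure is confined to the per-subject figures for secondary endpoints above the starting level, and whether it shows in print depends on shells that are not available here.

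**What to change.** In SAP 11.4, state that in by-level columns the percentage of subjects with a TEAE or local reaction is based on SAF subjects in the cohort who had at least one infusion at that level, that this N is printed in the column header, and that SAP 8.1.1 does not override it. Keep the full cohort SAF for the responder percentage and for Total columns. Check the table shells against this wording.

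As a minor clarification, say in SAP 11.1 that by-level percentages of valid infusions use the infusions at that level.

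The cost is a few sentences, through a SAP amendment as SAP 5 requires for changes after finalization, plus column Ns; no new data are needed. By-level percentages will look less favourable wherever fewer subjects enter, and they will be coarse: with 5 entrants one subject is 1/5 = 20 percentage points. The change makes each column describe its own level. It does not make levels comparable like for like, because entrants to higher levels are selected by success at lower ones; a short table note to that effect would help.
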